(Levels of PEEP in these FiO₂/PEEP scales represent levels set on the ventilator, not levels of total-PEEP, auto-PEEP, or intrinsic-PEEP.)

- (a) Minimum initial FiO₂/PEEP setting in the Higher ELV/Lower FiO₂ group will be .30/12.
- (b) FiO₂/PEEP setting may not be decreased from its initial level (compatible with the oxygenation goals) in the Higher ELV/Lower FiO₂ group for at least 12 hours after initial protocol ventilator adjustments. Arterial oxygenation may exceed goals during this initial 12hour interval.
- (c) **Recruitment maneuvers (RM)** will be performed in the Higher ELV/Lower FiO₂ group within one hour of the initial FiO₂/PEEP adjustments, once daily (between 0600-1000), after disconnections of the endotracheal tube from the ventilator circuit, and after coughing or agitation that causes (within 5 minutes) a sustained (≥ 10 minutes) decrease in SpO₂ of $\geq 5\%$ or in PaO₂ of ≥ 15 mmHg. No more than 4 recruitment maneuvers will be performed in any 24-hour interval. Each recruitment maneuver will be documented.

RMs will be performed as follows if systolic blood pressure = 100-200 mmHg, heart rate = 70-140, and there were < 4 RMs in the preceding 24 hours:

- (a) If FiO₂ < .90, FiO₂ will be raised to 0.90 for 5 minutes.
- (b) Ventilation mode will be changed to CPAP = most recent PEEP level.

- (c) CPAP will be increased over 10 seconds to 40 cmH₂O (to 45 cmH₂O if measured wt. \geq 150% PBW).
- (d) CPAP will be maintained at 40 (or 45) cmH₂O for 45 seconds.
- (e) The RM will be terminated immediately and CPAP returned to the most recent PEEP level if any of the following signs of distress occur:
 - Systolic blood pressure decreases to 90 mmHg or by > 30 mmHg.
 - Heart rate increases to > 140 /min or by > 20 /min.
 - SpO₂ decreases by 5% and is $< 90\%$
- (f) After 45 Seconds at CPAP = 40 (or 45) cmH₂O, CPAP will be decreased over 5 seconds to the pre-RM level.
- (g) Most recent ventilation settings (Mode, tidal volume, PEEP/FiO₂, etc) will be resumed upon completion or early termination of RM.
- (h) If 2 RMs require early termination within a single 24 hour interval, no additional RMs will be attempted for at least 12 hours.

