Arterial oxygenation will be assessed by either SpO₂ or PaO₂ at least every 4 hours. When SpO₂ is used to assess arterial oxygenation, the following measures will be taken if possible to improve accuracy: the SpO₂ sensor will be checked to ensure optimal position, cleanliness, and consistent readings with satisfactory waveforms; no position changes or endobronchial suctioning for at least 10 minutes; no invasive procedures or ventilator changes for at least 30 minutes. SpO₂ will be observed for a minimum of 1 minute, and a representative value will be recorded on the appropriate source-document flowsheet.

If arterial oxygenation is not within the target range, then either FiO₂ or PEEP will be adjusted within 30 minutes. Following these adjustments, oxygenation will be reassessed within 15 minutes and subsequent adjustments made if necessary.

If a patient's PEEP/FiO₂ is not compatible with the PEEP/FiO₂ scale (e.g. immediately after randomization or after urgent changes in FiO₂ or PEEP in response to desaturations, hypotension, etc.), either PEEP or FiO₂ (or both) will be

adjusted at intervals of 5-15 minutes (according to Appendix D) until the PEEP/FiO₂ is compatible with the scale.

In both treatment groups, if PaO₂ < 55 mmHg or SpO₂ < 88% and tidal volume = 4 ml/kg PBW (or the minimum tidal volume necessary for pH control, section 4b above) and plateau pressure ≥ 30 cmH₂O, then FiO₂ will be raised until PaO₂ = 55-80 mmHg or SpO₂ = 88-95% or FiO₂ = 1.0. If PaO₂ < 55 mmHg or SpO₂ < 88% and FiO₂ = 1.0, PEEP will be raised by 2 cmH₂O increments to 24 cmH₂O. In these circumstances, plateau pressure may exceed 30 cmH₂O.

Brief periods (5 minutes) of SpO₂ < 88% or > 95% may be tolerated without making changes in PEEP or FiO₂.

FiO₂ = 1.0 may be used for brief intervals (10 minutes) of transient desaturation or to prevent desaturation during treatments such as tracheo-bronchial suctioning or position changes.

If FiO₂ = 1.0 and PEEP = 24 cmH₂O and PaO₂ < 55 or SpO₂ < 88%, then a PEEP increase trial may be performed as follows:

- (a) Increase PEEP by 2-5 cmH₂O increments to a maximum of 34 cmH₂O or until PaO₂ = 55-80 mmHg or SpO₂ = 88-95%.
- (b) If the PEEP increase trial does not lead to an increase in PaO₂ of ≥ 5 mmHg within 4 hours, PEEP will be set = 24 cmH₂O.

In both study groups, in-line suction catheters will be encouraged to avoid unnecessary disconnections of the ventilator circuit from the endotracheal tube.

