event that is unexpected in the course of treatment for Acute lung Injury or ARDS.

Adverse events will be considered to be study-related if the event follows a reasonable temporal sequence from a study procedure and could readily have been produced by the study procedure.

Organ failures related to ARDS or a patient's underlying condition should not be reported as adverse events since they are systematically captured by the protocol data collection.

C Schedule of Events

D Procedures for PEEP and FiO₂ adjustments when PEEP/FiO₂ is not compatible with protocol.

- If arterial oxygenation is higher than the target range:
Either FiO₂ or PEEP will be decreased (by .10 or 2, respectively), whichever is farther (number of step changes) from the target scale .
If both PEEP and FiO₂ are equidistant from the scale, then:
 - Lower ELV/Higher FiO₂ Study Group: decrease PEEP first
 - Higher ELV/Lower FiO₂ Study Group: decrease FiO₂ first
- If arterial oxygenation is lower than the target range:
Either FiO₂ or PEEP will be increased (by .10 or 2, respectively), whichever is farther (number of step changes) from the target scale.
If both PEEP and FiO₂ are equidistant from the scale, then:
 - Lower ELV/Higher FiO₂ Study Group: increase FiO₂ first
 - Higher ELV/Lower FiO₂ Study Group: increase PEEP first
- If arterial oxygenation is within the target range:
If a single adjustment in either FiO₂ or PEEP would correct the FiO₂/PEEP to the target scale, then a change in either PEEP or FiO₂ will be made, following the study group priority sequence:
 - Lower ELV/Higher FiO₂ Group: decrease PEEP, increase FiO₂, decrease FiO₂, increase PEEP.
 - Higher ELV/Lower FiO₂ Group: increase PEEP, decrease FiO₂, increase FiO₂, decrease PEEP.

If the FiO₂/PEEP cannot be corrected to the target scale with a single adjustment, then FiO₂ will be adjusted by .10 and PEEP will be simultaneously adjusted in the opposite direction by 2 cmH₂O. E.g.: increase FiO₂ by .10 and decrease PEEP by 2 cmH₂O, or decrease FiO₂ by .10 and increase PEEP by 2 cmH₂O.

E Genetic Testing Information

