7. Elevated intracranial pressure (Appendix A), tricyclic antidepressant overdose (if most recent blood level is elevated or no blood level available), Hgb SS, Hgb SC, or conditions in which hypercapnia would **still** be contraindicated (attending physicians will be advised the hypercapnia may occur).

Prospective, Randomized, Multi-Center Trial of Higher
End-Expiratory Lung Volume/Lower FiO₂ versus Lower End-Expiratory
Lung Volume/Higher FiO₂ Ventilation in Acute Lung Injury and
Acute Respiratory Distress Syndrome

ALVEOLI

PROTOCOL AMENDMENT
January 25, 2000

Previous 7 amendments were dated October 7, 1999

AMENDMENT 8 (adopted January 13-14, 2000, ARDS Network Steering
Committee Meeting).

Page 25 of the July 20, 1999 (Version 1) Protocol, item #2, is amended to:

2. Lower EELV/Higher FiO₂ Group: FiO₂ ≤ .40.
Higher EELV/Lower FiO₂ Group: If PEEP ≤ 12 cmH₂O, FiO₂/PEEP will
be changed to .40/8 for ≤ 30 minutes. SpO₂ must remain ≥ 88%
during these 30 minutes. If SpO₂ decreases below 88% during these
30 minutes, the previous FiO₂/PEEP setting will be resumed. No
further efforts to wean will occur this day.

Page 25, the paragraph following item 6 is amended to:

"... If respiratory rate exceeds 35/min during the 5-minute CPAP trial, the
patient will resume A/C ventilation. In Higher EELV/Lower FiO₂ patients,
PEEP/FiO₂ will be returned to the Higher EELV/Lower FiO₂ settings that
existed prior to the change to 8/.40. The patient will be reassessed"

Page 27, section 4.1.2.4 (Subsequent ventilator settings during weaning), item 2
is amended to:

"2. If PS = 10, 15, or 20 cmH₂O is not tolerated, then return to A/C at
PEEP/FiO₂ appropriate to Study Group assignment."

Prospective, Randomized, Multi-Center Trial of
Higher End-Expiratory Lung Volume/Lower FiO₂ versus
Lower End-Expiratory Lung Volume/Higher FiO₂ Ventilation in
Acute Lung Injury and Acute Respiratory Distress Syndrome

ALVEOLI

PROTOCOL AMENDMENT (May 15, 2000)

These amendments were adopted by the ARDS Network Steering Committee on May 15, 2000. The first amendment is designed to achieve greater separation between the study groups in mean PEEP levels. The subsequent amendment is designed to allow both study groups to begin to wean at the same level of oxygenation impairment (FiO₂/PEEP requirement).

I. Page 22 of the July 20, 1999 (Version I) Protocol is amended as follows:

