1. In the Higher EELV/Lower FiO₂ study group, the following three FiO₂/PEEP combinations are deleted from the low-end of the FiO₂/PEEP scheme: .30/5, .30/8, .30/10.
2. Clause (b), first sentence: "FiO₂/PEEP setting may not be decreased from its initial level ... in the Higher ELV/Lower FiO₂ group for at least 12 hours after initial protocol ventilator adjustments" is amended to read as follows:
 - (b) FiO₂/PEEP setting may not be decreased below .30/14 in the Higher EELV/Lower FiO₂ group (except for possible weaning as described in the subsequent amendment to section 4.1.2.1.2) during the first 48 hours after initial protocol ventilator adjustments. FiO₂/PEEP setting may not be decreased below .30/12 in the Higher EELV/Lower FiO₂ group (except for possible weaning as described in the subsequent amendment to section 4.4.2.1.2) after 48 hours until 28 days elapse from initiation of protocol ventilator procedures.

II. Page 25, Section 4.1.2.1.2 is amended as follows to allow both study groups to begin to wean if arterial oxygenation can be maintained at or above the target range on FiO₂/PEEP of .40/8. This amendment supercedes a previous amendment dated January 14, 2000:

2. Lower EELV/Higher FiO₂ Group: FiO₂/PEEP ≤ .40/8.

Higher EELV/Lower FiO₂ Group:

- From 12-48 hours after initiation of protocol ventilator procedures: If FiO₂ ≤ .30 and PEEP = 14, FiO₂/PEEP will be changed to .40/8. SpO₂ must remain ≥ 88% for 30 minutes at FiO₂/PEEP = .40/8. If SpO₂ falls below 88%, previous FiO₂/PEEP settings will be resumed. (Recruitment Maneuvers will be conducted as defined in Section 4.1.1 after returning to previous FiO₂/PEEP settings if SpO₂ < 88% during the trial at FiO₂/PEEP = .40/8).
- 48 hours-28 days after initiation of protocol ventilator procedures: If FiO₂ ≤ .30 and PEEP = 12, FiO₂/PEEP will be changed to .40/8. SpO₂ must remain ≥ 88% for 30 minutes at FiO₂/PEEP = .40/8. If SpO₂ falls below 88%, previous FiO₂/PEEP settings will be resumed. (Recruitment Maneuvers will be conducted as defined in Section 4.1.1 after returning to previous FiO₂/PEEP settings if SpO₂ < 88% during the trial at FiO₂/PEEP = .40/8).

The following addition in **bold face type** is a clarification of intent of the July 20, 1999 Version I of the protocol

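### The May 2000 amendment leaves the Higher-arm minimum start at .30/12, below its own 48-hour floor of .30/14 and outside its 12–48 h weaning trigger

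*Supplement*

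**What the plan says.** Section 4.1.1, item 4, clause (a): "Minimum initial FiO₂/PEEP setting in the Higher ELV/Lower FiO₂ group will be .30/12".

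The amendment of May 15, 2000, part I, makes two changes to that page. Item 1 says that three "combinations are deleted from the low-end of the FiO₂/PEEP scheme: .30/5, .30/8, .30/10", so .30/12 stays on the Higher-arm scale. Item 2 rewrites the first sentence of clause (b): "FiO₂/PEEP setting may not be decreased below .30/14 in the Higher EELV/Lower FiO₂ group" during the first 48 hours, with weaning as the only exception; after 48 hours the floor is .30/12. Clause (a) is not mentioned.

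Part II replaces weaning criterion 2 in Section 4.1.2.1. For the Higher arm from 12 to 48 hours: "If FiO₂ ≤ .30 and PEEP = 14, FiO₂/PEEP will be changed to .40/8". From 48 hours to day 28 the same test applies at PEEP = 12. The Lower-arm rule is an inequality, at or below .40/8.

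The introduction gives the aim of part I: "The first amendment is designed to achieve greater separation between the study groups in mean PEEP levels". Part II states its own: "to allow both study groups to begin to wean if arterial oxygenation can be maintained at or above the target range" on .40/8. The amendment of October 12, 2000 removes recruitment maneuvers and leaves all of these rules as they stand.

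**The concern.** The lowest permitted start and the floor for the first 48 hours differ by one step, and the weaning trigger is tied to the floor by an equals sign. A mild patient can properly start on .30/12, stay there, and fall outside the 12–48 h trigger because PEEP is too low rather than too high.

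Two things are at stake. PEEP separation is reduced in the period when the floor is highest. Weaning entry is delayed in one arm only, which can feed into ventilator-free days and secondary outcomes 5 and 6 (days from first meeting the weaning criteria, and from first unassisted breathing, to day 28). Sites that resolve the conflict differently will also treat the same patient differently, and the daily check of ventilator settings (Section 5.3.1) has no single rule to check against.

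**Working it through.** The plan gives no figure on this point, so there is none to reproduce. The check sets the rules in force side by side and then sizes the effect.

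**1. Low Higher-arm steps against the rules in force**

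| FiO₂/PEEP | Permitted start, clause (a) | At or above 48 h floor | 12–48 h trigger | Trigger after 48 h |
|---|---|---|---|---|
| .30/12 | yes | no | no | yes |
| .30/14 | yes | yes | yes | no |
| .40/14 | yes | yes | no | no |

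**2. Can a patient reach .30/12?** Yes. With oxygenation in range, Appendix D first tries a single adjustment that lands on the scale (Higher arm: PEEP up, FiO₂ down, FiO₂ up, PEEP down). Failing that, "then FiO₂ will be adjusted by .10 and PEEP will be simultaneously adjusted in the opposite direction by 2 cmH₂O". Taking FiO₂ down and PEEP up:
- .40/10 → .30/12
- .40/8 → .30/10 (now deleted) → .30/12
- .50/8 → .40/10 → .30/12
- for contrast, .50/10 → .40/12 → .40/14

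**3. Does any rule then raise the patient?** No. Section 4.1.1 says: "If arterial oxygenation is not within the target range, then either FiO₂ or PEEP will be adjusted within 30 minutes". Appendix D applies when the setting is off the scale. A patient in range on .30/12 meets neither condition.

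**4. Mornings lost under the literal trigger.** The window is 48 − 12 = 36 hours and assessments are daily. It therefore holds 1 or 2 mornings, with mean 36/24 = 1.5 over start times.

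**5. Weaning criterion 3** (Section 4.1.2.1) also requires PEEP and FiO₂ no higher than the previous day's reference values. Let h be the hour of the first morning at or after hour 12, with mornings 24 hours apart.
- If 12 ≤ h < 24, the window holds two mornings, and the previous morning fell before the start. If that pre-protocol value counts and was PEEP 8 or 10, PEEP 12 exceeds it and the first morning is blocked whatever the trigger says. One remains.
- If 24 ≤ h < 36, the window holds one morning, and the previous one already fell on protocol settings. One remains.

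On that assumption the trigger itself costs about one morning rather than 1.5. Whether a day-0 reference value exists depends on Appendix C, whose content is not shown.

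**6. Would such a patient pass the .40/8 test?** Take PaO₂ 55 mmHg as the counterpart of SpO₂ 88%, as the paired target limits suggest. In range on .30 means PaO₂/FiO₂ from 55/.30 = 183 to 80/.30 = 267. The test needs 55/.40 = 137.5. The patient passes unless going from PEEP 12 to 8 lowers the ratio by more than 1 − 137.5/183.3 = 25% (at PaO₂ 55) to 1 − 137.5/266.7 = 48% (at PaO₂ 80).

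**7. PEEP separation per affected patient**
- Lower-arm comparator on .40/8: 12 − 8 = 4 instead of 14 − 8 = 6 cmH₂O (33% less).
- Lower-arm comparator on PEEP 5: 12 − 5 = 7 instead of 14 − 5 = 9 cmH₂O (22% less).

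**8. Arm level.** The share s of the Higher arm starting on .30/12 is not given. Assume 5%, 10% or 20%, all staying there for 48 hours.
- Mean PEEP in the first 48 hours is lower by 2s = 0.1, 0.2 or 0.4 cmH₂O.
- Mean weaning delay is at most 1.5s = 0.075, 0.15 or 0.30 day. If criterion 3 blocks the first morning as in step 5, it is at most 1.0s = 0.05, 0.10 or 0.20 day.

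Both delay figures are upper bounds, since a lost morning costs a day only if the patient would also have passed the .40/8 test, the CPAP trial and the later weaning steps.

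**The case against.** The best answer is that the amendment points to one sensible reading. It is later than clause (a), it aims at greater PEEP separation, it names weaning as the only exception to the floor, and its two triggers match its two floors. A site could reasonably take .30/14 as the lowest setting for 48 hours and treat clause (a) as leftover text. On that reading nobody is shut out and every figure above is zero. This stands as a likely intention, but no text says it. Clause (b) bars decreasing below .30/14; it does not bar starting or staying below it.

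Three stronger readings are tempting and are not supported:
- *A start on .30/12 breaches the protocol.* It does not. Clause (a) permits it, and clause (b) restricts decreases only.
- *A patient who worsens and is moved up to .30/14 gets the test, while the milder one on .30/12 does not.* This holds only if criterion 3 is also met. If the rise falls between two morning reference measurements, PEEP 14 exceeds the previous day's 12 and that morning is blocked too. For the same reason, raising PEEP at the bedside to meet the trigger is not a clean way round.
- *Separation falls by a third.* That depends on choosing a Lower-arm patient on .40/8; against PEEP 5 the loss is 22%.

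It is also fair to say that the two proposed edits overlap. Once clause (a) reads .30/14, the second matters only for patients already on .30/12.

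**Conclusion.** The conflict is real in the text now in force. Followed as written, the rules allow a Higher-arm patient to run 2 cmH₂O under the 48-hour floor and withhold the .40/8 test until 48 hours, against both stated aims of the amendment. The cost is at most one or two morning assessments per affected patient, and can be fewer because of criterion 3.

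The reach is limited. Only patients adequately oxygenated on .30/12 are concerned; their number is not given and is probably small, and the arm-level figures rest on assumed shares of 5–20%. A reader might infer that the mortality comparison or its power is undermined. The documents do not support that: the primary endpoint definition, the sample size and the stopping boundaries do not depend on these rules. It should be corrected because it concerns how the intervention and weaning entry are defined, and the correction is easy.

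**What to change.** Make two edits:
- Clause (a): set the minimum initial FiO₂/PEEP in the Higher arm at .30/14.
- Part II, 12–48 h rule: write the trigger as FiO₂ ≤ .30 and PEEP ≤ 14, so that any patient already on .30/12 is covered.

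Leave the floors, the trigger after 48 hours, criterion 3 and the Lower-arm rule as they are. The second edit does not recover a morning that criterion 3 blocks.

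No extra patients or data are needed, and the weaning standard is not loosened, since the wider trigger adds only patients who need less PEEP than those already tested. The downside is that mild patients receive 2 cmH₂O more PEEP for 48 hours, with its circulatory risk; clause (b) already intends this. Patients started on .30/12 before the change remain as treated.
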